5.5.3 Other efficacy endpoints

- Changes from baseline to time window Visit 5 (Week 2) and time window Visit 6 (Week 4) of DB treatment period (Period II) in mean trough SiSBP and SiDBP (measured by OBPM);
- Change from baseline to Week 8 of DB treatment period (Period II) in mean daytime ABPM;
 - *Change from baseline in mean daytime DBP.* All ABPM measurements taken between 09:00 and 21:00 will be included in this calculation [O'Brien 2013]; there may be two parts of the daytime DBP-time curve to be considered for a subject at a given visit, one for each calendar day of Visits 4 and 7. At each visit the mean daytime DBP will be derived from the area under the DBP-time curve(s), divided by the time span(s) [see Appendix B for clarification]. The change from baseline to Week 8 will be obtained as the difference in mean daytime DBP ABPM between Visit 7 and Visit 4.
 - *Change from baseline in mean daytime SBP.* Similar to change from baseline in mean daytime DBP.

[figure not shown]
- Change from baseline to Week 8 of DB treatment period (Period II) in mean night time ABPM;
 - *Change from baseline in mean night time DBP.* All ABPM measurements taken between 01:00 and 06:00 will be included in this calculation [O'Brien 2013]; there should be one night time part of the DBP-time curve to be considered for each subject at a given visit; in the unlikely event that there are two, only the first one will be used). At each visit the mean night time DBP will be derived from the area under the DBP-time curve, divided by the time span [see Appendix B for further specification]. The change from baseline to Week 8 will be obtained as the difference in mean daytime DBP ABPM between Visit 7 and Visit 4.
 - *Change from baseline in mean night time SBP.* Similar to change from baseline in mean night time DBP.
- Trough to peak ratio for SBP based on ABPM;
 - The trough to peak ratio for SBP will be derived on treatment group level based on the time course of ABPM as similar to the trough to peak ratio for DBP.
- Changes from baseline to time window Visit 8 (Week 10 i.e., Week 2 of withdrawal period - Period III) in mean trough SiSBP and SiDBP (measured by OBPM);
- Changes from Week 8 of Period II to time window Visit 8 (Week 10 i.e., Week 2 of withdrawal period - Period III) in mean trough SiSBP and SiDBP (measured by OBPM).

5.5.3.1 Illustration of derivation of ABPM endpoints

The derivation of the various endpoints based on ABPM is illustrated by means of an example. Figure 1 displays the DBP and SBP measured by ABPM in one subject at one visit. The data underlying this example figure are included in Appendix B.

Since ABPM measurements are obtained during 24 hours at two consecutive calendar days, the time on the horizontal axis runs from 0–48 hours, clock times 0:00–23:59 corresponding to the first day and times 24:00–48:00 to the second day. The ABPM started on 10:29 on the first day and finished on 11:04 on the second day [35:04 in Appendix B].

Figure 1 Example DBP and SBP measured by ABPM

Example DBP (blue lines) and SBP (red lines) measured by ABPM in one subject at one visit. Vertical lines indicate inclusion of measurements in the calculation of daytime ABPM (solid) and night time ABPM (dotted).

The derivation of the 24-hour mean DBP (SBP), mean daytime DBP (SBP) and mean night time DBP (SBP) for these example data are as follows.

- The total duration of this ABPM (24 hours 35 minutes) was greater than 24 hours, but less than 25 hours, so all measurements were included in the calculation of 24-hours mean ABPM.
- The 24-hour mean DBP (SBP) is derived from the area under the DBP (SBP) curve, divided by the time span. The area under the curve is calculated by the trapezoidal rule. The implementation of this rule in SAS is given in Appendix B. For the example data the areas under the DBP and SBP curves are 8,640,870 and 12,956,970 mmHg sec, respectively. Dividing both areas by the time span of

88,500 sec gives a 24-hour means of 97.6 and 146.4 mmHg for DBP and SBP, respectively.

- The trapezoidal rule will be applied up to the last measurement within 25 hours. If there is another measurement after 25 hours, there will be NO interpolation up to 25 hours exactly.
- The mean daytime DBP (SBP) is based on two periods: from 10:29 to 21:00 (limits included) on the first day and from 09:00 to 11:04 on the second day (limits included; 33:00 to 35:04 in Appendix B). The mean daytime DBP and SBP are 99.5 mmHg and 143.9 mmHg, respectively.
- The mean night time DBP (SBP) is based on the measurements between 01:00 and 06:00 on the second day (limits included; 25:00 to 30:00 in Appendix B). The mean night time DBP and SBP are 78.4 mmHg and 135.5 mmHg, respectively.
- Note that measurements between 21:00 on the first day and 01:00 on the second day (limits excluded) and between 06:00 and 09:00 on the second day (limits excluded) are only included in the calculation of the 24-hour means, but not in the calculation of the daytime or night time means.

5.6 Safety variables

All assessments are considered and re-assigned to the most appropriate visit according to the time windows described in Section 11; reference to visits are to be intended as references to re-mapped visit, i.e., time window visits.

The following safety variables will be evaluated:

- Treatment-emergent adverse events (AEs);
- AEs leading to premature discontinuation of study treatment;
- Treatment-emergent deaths;
- Treatment-emergent serious adverse events (SAEs);
- Treatment-emergent electrocardiogram (ECG) abnormalities;
- Treatment-emergent marked laboratory abnormalities;
- Changes from baseline to time window Visits 5, 6 and 7 (Weeks 2, 4 and 8, respectively) of DB treatment period (Period II) in laboratory parameters;
- Changes from baseline to time window Visits 6 and 7 (Week 4 and Week 8, respectively) of DB treatment period (Period II) in ECG parameters (pulse rate [PR], QRS, QT, QTcB, QTcF);
- Changes from baseline to time window Visits 5, 6 and 7 (Weeks 2, 4 and 8, respectively) of DB treatment period (Period II) in body weight and PR (BpTRU[®]).

5.6.1 Adverse events

An AE is defined as any term reported by the investigator in the **Adverse Event** eCRF. The original terms used by the investigators to describe AEs are assigned preferred terms for classification and tabulation using the MedDRA dictionary, Version 19.0.

5.6.1.1 Treatment-emergent adverse events

Double-blind treatment-emergent AEs are defined as those AEs with onset on or after the double-blind treatment start date [see definition in Section 11.2] up to the double-blind treatment end date [see definition in Section 11.4] plus 30 days (included). Run-in treatment-emergent AEs are AEs with onset dates between the start and end dates of the run-in placebo (or the start of double-blind treatment, if applicable; limits included).

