8.1.2 Visit 2 / Week -4

This visit will be performed only for subjects who had anti-hypertensive drugs at Visit 1.

The visit will be performed at Day -28 ± 3 days.

The subject must not take study treatment at home on the morning of Visit 2.

Visit 2 includes:

- Sitting BP and HR, and standing BP, measured by OBPM device at trough.
- Physical examination and body weight.
- *Urine pregnancy test for women of childbearing potential.
- Reporting of AEs and SAEs.
- Recording of changes in concomitant medications.
- *Assessment of childbearing potential and recording of changes in contraception methods, if applicable.
- *Record the date and time of last study treatment intake before this visit.
- *Check compliance with study treatment.

The investigator checks the exclusion criteria and the following eligibility criterion and decides on the potential eligibility of the subject for the next visit (Visit 3):

- o mean SiDBP measured by OBPM device < 110 mmHg
- 1) If this criterion is not met, the subject must be discontinued from the study. In such case, tests highlighted by * are optional and performed as deemed necessary per medical practice. The investigator has to record the reason of the run-in failure in the eCRF. A follow-up telephone call must be performed in 2 weeks to check any potential AEs/SAEs.
- 2) If the criterion is met, study treatment must be taken at site (i.e., one capsule from each bottle) from the bottles dispensed at Visit 1. Record the study treatment intake date and time. Retrieve the 2 bottles.

Essential hypertension Protocol AC-080A201 Version 3 30 May 2016, page 68/112

Confidential

- Access IRT to get bottle numbers.
- Dispense 2 new bottles, and instruct subject to take one capsule from each bottle irrespective of food intake every morning between 7:00 and 10.00 a.m.
- Remind the subject to bring back both bottles to the next visit and not take study treatment on the day of study visit prior to coming to the site.

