10 SAFETY DEFINITIONS AND REPORTING REQUIREMENTS

10.1 Adverse events

10.1.1 Definitions of adverse events

An AE is any adverse change, i.e., any unfavorable and unintended sign, including an abnormal laboratory finding, symptom, or disease that occurs in a subject during the course of the study (i.e., from signing of the informed consent), whether or not considered by the investigator as related to study treatment.

A treatment-emergent AE is any AE temporally associated with the use of study treatment (from study treatment initiation in run-in period until 30 days after study treatment discontinuation) whether or not considered by the investigator as related to study treatment.

Adverse events include:

- Exacerbation of a pre-existing disease.
- Increase in frequency or intensity of a pre-existing episodic disease or medical condition.
- Disease or medical condition detected or diagnosed during the course of the study even though it may have been present prior to the start of the study.
- Continuous persistent disease or symptoms present at study start that worsen following the start of the study (i.e., signing of informed consent).
- Abnormal assessments, e.g., change on physical examination, ECG findings, if they
 represent a clinically significant finding that was not present at study start or
 worsened during the course of the study.
- Laboratory test abnormalities if they represent a clinically significant finding, symptomatic or not, which was not present at study start or worsened during the course of the study or led to dose reduction, interruption or permanent discontinuation of study treatment.

Overdose, misuse, and abuse of the study treatment should be reported as an AE and, in addition, study treatment errors must be documented in the study drug accountability log of the eCRF.

Essential hypertension Protocol AC-080A201 Version 3 30 May 2016, page 78/112

Confidential

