11.3.5.1 Adverse events

A treatment-emergent AE is any AE temporally associated with the use of a study drug. Treatment-emergent is defined as in Section 10.1.1. The number and percentage of subjects experiencing treatment-emergent AEs and SAEs at least once will be tabulated by treatment group and by:

- MedDRA System Organ Class (SOC) and individual Preferred Term (PT) within each SOC, in descending order of incidence.
- Frequency of subjects with events coded with the same PT, in descending order of incidence.

Furthermore, treatment-emergent AEs and SAEs will be tabulated as described above by severity and relationship to study drug.

Essential hypertension Protocol AC-080A201 Version 3 30 May 2016, page 89/112

Confidential

AEs leading to premature discontinuation of study drug and death will also be summarized as described above.

Listings will be provided for all reported AEs, including SAEs. In addition, separate listings will be provided for SAEs, for AEs leading to premature discontinuation of study drug, and for AEs leading to death.

The number and percentage of subjects with treatment-emergent ECG abnormalities will be tabulated by treatment group.

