11.3 Run-in treatment end date/time

The run-in treatment end date is the last day of intake of run-in study treatment. It is derived from the last DB treatment end date (in chronological order) in the **Study Drug Log** eCRF where the 'Study Period' is 'SB RUN-IN'. If the end time of the run-in period is missing, it will be set to the start time of the DB period minus 1 minute, in the event that the DB period is missing it will be set to 23:59.

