11.5 Double-blind treatment start date/time

It is the first day of intake of study treatment during the double-blind period. It is derived from the first treatment start date (in chronological order) in the **Study Drug Log** eCRF where the 'Study Period' is 'DB TREATMENT'.

If the date is missing the randomization date (see definition below) is used. If the subject is listed as run-in failure [see definition in Section 5.1] the date is set to ‘missing’. If the start time of the double-blind treatment is missing and the start date of DB period corresponds to the date of Randomization, the Randomization time will be used. In other cases the start time of DB will be set to 00:00.

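### For subjects who fail the run-in, the SAP closes the treatment-emergent window on the last placebo day, so events starting at the failing visit or before the 2-week call are left out of the run-in AE and SAE tables

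*SAP*

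**What the plan says.** **SAP, run-in window.** Section 5.6.1.1: "Run-in treatment-emergent AEs are AEs with onset dates between the start and end dates of the run-in placebo", with the bracketed addition "or the start of double-blind treatment, if applicable; limits included". Sections 5.6.2 (deaths) and 5.6.3 (SAEs) use the same window.

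**SAP, the dates behind it.** Section 11.3: "The run-in treatment end date is the last day of intake of run-in study treatment". A missing end time for a subject with no double-blind period becomes 23:59, which adds no days. Section 11.5, on the double-blind start: "If the subject is listed as run-in failure [see definition in Section 5.1] the date is set to" missing.

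**SAP, double-blind window.** The same paragraph of 5.6.1.1 defines double-blind treatment-emergent AEs as "those AEs with onset on or after the double-blind treatment start date", up to the end of double-blind treatment plus 30 days.

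**Protocol.** Section 10.1.1 defines treatment-emergence as running "from study treatment initiation in run-in period until 30 days after study treatment discontinuation". Section 11.3.5.1 adopts this for the analysis: "Treatment-emergent is defined as in Section 10.1.1".

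**Dosing around visits.** Protocol 8.1.2: "The subject must not take study treatment at home on the morning of Visit 2". Section 8.1.3 repeats this for Visit 3 and has subjects reminded of it for Visit 4. In 8.1.2, 8.1.3 and 8.1.4.1, placebo is given at the site only when the visit's criteria are met. A subject who fails is discontinued and must be called two weeks later about AEs and SAEs.

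**The concern.** The SAP keeps a 30-day tail for the double-blind period and drops it for the run-in. For randomized subjects this costs nothing, because their run-in window reaches the first double-blind dose. For subjects who stop during the run-in, the window closes with the last capsule, so the event that coincides with or follows the stop can fall outside it. SAP 4.1 lists the changes from the protocol and does not include this one.

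The run-in includes withdrawal of existing antihypertensive treatment, and protocol 10.1.4 gives exacerbation after wash-out as its example of an AE caused by the study design. The run-in tables in SAP 13.9.1, 13.9.3 and 13.9.4 (overview, AEs by preferred term, SAEs, AEs leading to discontinuation) are all restricted to run-in treatment-emergent events. They can undercount that harm in the subjects who stopped at a visit.

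Two smaller errors belong to the same rules:

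- For randomized subjects both windows include the double-blind start date, so a Day 1 onset is counted in both periods.
- SAP 10.9.2.1 says all deaths are listed with their period, run-in included. SAP 13.9.2 restricts the listing to the Safety Set, which by 7.1.6 requires a Period II dose.

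**Working it through.** The plan gives no figure to reproduce, so the check is date logic plus simple counts.

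**1. Window for a subject stopped on a criterion.** Let V be the day of the failing visit (2, 3 or 4).

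- No home dose on the morning of V, and no site dose because a criterion failed: last intake = V − 1.
- SAP window: run-in start to V − 1.
- Mandated call: about V + 14.
- Protocol 10.1.1 window: run-in start to (V − 1) + 30 = V + 29.

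**2. Days followed but not counted.**

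| Onset | Followed for AEs? | In SAP window? | In protocol window? |
|---|---|---|---|
| Up to V − 1 | Yes | Yes | Yes |
| V (visit day) | Yes | No | Yes |
| V + 1 to V + 14 | Yes, by the call | No | Yes |
| V + 15 to V + 29 | No planned contact | No | Yes |

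Followed days after the last dose: 1 + 14 = 15. The SAP counts 0 of them. The protocol window after the last dose is 30 days, so the data in hand cover 15/30 = 50% of it.

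Onset date decides, not report date. An event first mentioned at the visit or call but with onset on or before V − 1 is still counted. So is a first grade 3 reading confirmed later under protocol 5.1.12 A while dosing continued.

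**3. Subjects under the truncated window.** The upper bound is everyone who enters and is not randomized. Protocol 3.1 gives about 640 enrolled; the synopsis and SAP 2.1 give about 1000. The randomization target is 540, lowered to 490 (SAP 4.2).

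| Enter | Randomized | Not randomized |
|---|---|---|
| 640 | 540 | 640 − 540 = 100 (16%) |
| 640 | 490 | 640 − 490 = 150 (23%) |
| 1000 | 540 | 1000 − 540 = 460 (46%) |
| 1000 | 490 | 1000 − 490 = 510 (51%) |

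These count subjects, not events. Many will fail for reasons other than harm, such as SiDBP below 90 mmHg or compliance below 80% at Visit 4. The documents do not split failures by reason and give no AE rate for these days.

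**4. Day 1 overlap.** The run-in window runs up to and including the double-blind start, and the double-blind window opens on that date. Each randomized subject has 1 day in both.

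**The case against.** The best defence is protocol 11.3.5, which asks for summaries of safety data from Period I. The 10.1.1 definition is study-wide and has no run-in-specific part, so the SAP had to split it by period, and ending the run-in part with placebo intake is a natural choice. In addition, protocol 10.1.5 and 10.2.2 tie the end of AE reporting to double-blind discontinuation, which these subjects never have. A full 30-day tail could not be filled. The extra days are off placebo, possibly on drugs forbidden during the study, and say nothing about the four ACT-132577 doses.

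This does not save the rule. The failing visit belongs to Period I on any reading and is still excluded. Later onsets are treatment-emergent under 10.1.1 yet fall in no SAP window at all. If a shorter window was meant, SAP 4.1 should say so.

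Several parts of the defence stand and limit the size:

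- A subject dosed at Visit 3 and later excluded on that visit's laboratory results keeps that day's onset in the window; only later onsets are lost.
- The 150 and 510 figures pair planned enrolment with the revised 490, a combination no document states.
- The Day 1 overlap falls across separate tables on different sets, so no single total is inflated.
- No run-in death table is planned, so the truncated window in 5.6.2 changes no death table. A fatal event is also an SAE and appears in the SAE listing on the Run-in Set.
- AEs and SAEs stay in listings on the Run-in Set, and AEs leading to discontinuation in a listing on the Screened Set. The stops themselves are counted in the tables of reasons for run-in failure, run-in treatment discontinuation and study discontinuation before randomization.

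**Conclusion.** The concern holds and is minor. For a subject stopped on a criterion at Visit 2, 3 or 4, the SAP window counts none of the 15 days followed after the last dose, whereas the protocol definition counts all of them, and the difference is not declared. At most 100 to 510 subjects come under the truncated window, depending on which planning figures are used; the number of events lost cannot be derived from the documents. The visit-day part assumes that the dosing instructions were followed and that the subject failed a blood pressure or compliance criterion at the visit.

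The affected outputs are descriptive placebo tables with one total column. Dose-response and between-group conclusions do not change. The Day 1 overlap and the death-listing population are real but small.

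**What to change.** - In SAP 5.6.1.1, 5.6.2 and 5.6.3, for subjects who do not enter double-blind treatment, end the run-in window at the run-in treatment end date plus 30 days, as in protocol 10.1.1. In practice this reaches the 2-week call.
- For randomized subjects, end the run-in window just before the first double-blind dose, so that a Day 1 event belongs to the double-blind period only.
- In SAP 13.9.2, produce the death listing on the Run-in Set or Screened Set, to agree with 10.9.2.1.
- If the shorter window is intended, declare it in SAP 4.1.3 and give the reason.

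The cost is SAP wording, one date derivation and one population label, on data already collected. Run-in counts may rise slightly for run-in failures and fall slightly for Day 1 events.

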5.6.1.2 Frequency of treatment-emergent adverse events

Except otherwise specified, the counting of treatment-emergent AEs in the summary table is handled as follows:

- Subjects who experienced the same AE more than once (as qualified by the same preferred term[s]) are counted only once.
- In the event that the reported AE is assigned to several preferred terms, subjects are counted for each individual preferred term.

5.6.1.3 Intensity of treatment-emergent adverse events

The intensity of an AE is determined by the investigator as ‘mild’, ‘moderate’ or ‘severe’.

AEs reported more than once (as qualified by the same preferred term) for a subject within a specified time period but with different intensities are counted only once, with the worst reported intensity in the corresponding analysis. If intensity is missing, the event is considered severe.

5.6.1.4 Relationship of treatment-emergent adverse events

Relationship to study treatment is determined by the investigator as ‘related’ or ‘not related’. An event is considered related if the response to the question ‘Relationship to study treatment?’ is answered ‘Related’.

For AEs reported more than once (as qualified by the same preferred term) for a subject within a specified time period, the worst relationship reported is taken. AEs with missing relationship are considered in any analysis as ‘Related’.

5.6.2 Deaths

Death information is taken from the **Death** eCRF. The primary cause of death is reported on the same form.

The original terms used by the investigators to describe the primary death cause are assigned preferred terms for classification and tabulation using the MedDRA dictionary.

Double-blind treatment-emergent deaths are those with occurrence on or after the double-blind treatment start date [see definition in Section 11.2] up to the double-blind treatment end date [see definition in Section 11.4] plus 30 days (included). Run-in

treatment-emergent deaths are deaths that occur between the start and end of the run-in placebo (or the start of double-blind treatment, if applicable; limits included).

5.6.3 Serious adverse events

An SAE is defined as an AE with “Serious?” = “Yes” on the **Adverse Events** eCRF.

Double-blind treatment-emergent SAEs are all SAEs with onset on or after the double-blind treatment start date [see definition in Section 11.2] up to the double-blind treatment end date [see definition in Section 11.4] plus 30 days (included). Run-in treatment-emergent SAEs are SAEs with onset date between the start and end dates of the run-in placebo (or the start of double-blind treatment, if applicable; limits included).

